8.3.2. Method of Detecting Adverse Events and Serious Adverse Events

Care will be taken not to introduce bias when detecting AEs or SAEs. Open-ended and nonleading verbal questioning of the participant is the preferred method to inquire about AE occurrence.

Solicited Adverse Events

Solicited AEs are predefined local and systemic events for which the participant is specifically questioned.

Unsolicited Adverse Events

Unsolicited AEs are all AEs for which the participant is not specifically questioned.

8.3.3. Follow-up of Adverse Events and Serious Adverse Events

The investigator is obligated to perform or arrange for the conduct of supplemental measurements and evaluations as medically indicated to elucidate the nature and causality of the AE, SAE, or PQC as fully as possible. This may include additional laboratory tests or investigations, histopathological examinations, or consultation with other health care professionals.

AEs, including pregnancy, will be followed by the investigator as specified in Section [10.6](#).

8.3.4. Regulatory Reporting Requirements for Serious Adverse Events

The sponsor assumes responsibility for appropriate reporting of AEs to the regulatory authorities. The sponsor will also report to the investigator (and the head of the investigational institute where required) all suspected unexpected serious adverse reactions (SUSARs). The investigator (or sponsor where required) must report SUSARs to the appropriate Independent Ethics Committee/Institutional Review Board (IEC/IRB) that approved the protocol unless otherwise required and documented by the IEC/IRB. A SUSAR will be reported to regulatory authorities unblinded. Participating investigators and IEC/IRB will receive a blinded SUSAR summary, unless otherwise specified.

8.3.5. Pregnancy

All initial reports of pregnancy in female participants or partners of male participants must be reported to the sponsor by the study site personnel within 24 hours of their knowledge of the event using the appropriate pregnancy notification form. Abnormal pregnancy outcomes (eg, spontaneous abortion, fetal death, stillbirth, congenital anomalies, ectopic pregnancy) are considered SAEs and must be reported using a SAE reporting form. Any participant who becomes pregnant during the study must promptly discontinue further study intervention. Participants who are found to be pregnant in between study visits should immediately stop taking the study intervention and contact the investigator.

Follow-up information regarding the outcome of the pregnancy and any postnatal sequelae in the infant will be required.

8.3.6. Disease-Related Events and Disease-Related Outcomes Not Qualifying as Adverse Events or Serious Adverse Events

All events that meet the definition of a SAE will be reported as SAEs, regardless of whether they are protocol-specific assessments.

8.3.7. Adverse Events of Special Interest

An adverse event of special interest (AESI; serious or non-serious) is one of scientific and medical concern specific to the sponsor's product or program, for which ongoing monitoring and expedited communication (within 24 hours) by the investigator to the sponsor is warranted. The AESIs for JNJ-77242113 are, active TB, malignancy, and potential Hy's Law cases.

Any newly identified malignancy, case of active TB, or potential Hy's law case occurring after the first study intervention administration(s) must be reported by the investigator according to the procedures in Section 10.6). Investigators are also advised that active TB is considered a reportable disease in most countries. These events are to be considered serious only if they meet the definition of an SAE.

8.4. Pharmacokinetics

Plasma samples will be used to evaluate the PK of JNJ-77242113. Plasma collected for PK may additionally be used to evaluate safety or efficacy aspects that address concerns arising during or

after the study period. Genetic analyses will not be performed on these plasma samples. Participant confidentiality will be maintained.

8.4.1. Evaluations

Venous blood samples for determination of JNJ-77242113 plasma concentrations will be collected at the time points indicated in the SoA (Section 1.3). During the study, the nominal sample collection times may be changed by the sponsor with clear communication to the investigator, but the total blood volume will not exceed 450 mL every 8 weeks. The exact dates and times of blood sample collection must be recorded in the CRF or on the laboratory requisition form.

The laboratory manual contains further information regarding the collection, handling, labeling, and shipment of plasma samples.

8.4.2. Analytical Procedures

Pharmacokinetics

Plasma samples will be analyzed to determine concentrations of JNJ-77242113 using a validated, specific, and sensitive liquid chromatography-tandem mass spectrometry (LC-MS/MS) method by or under the supervision of the sponsor. The sponsor, or its designee, under conditions in which the participants' identity remains blinded, will assay these samples.

8.4.3. Pharmacokinetic Parameters and Evaluations

Parameters

Pharmacokinetic analysis will be performed by or under the responsibility of the sponsor.

Using the actual sampling times (see the SoA [Section 1.3]), if feasible, the following pharmacokinetic parameters will be estimated for JNJ-77242113 using a population PK approach:

C_{\max}	Maximum observed plasma analyte concentration.
t_{\max}	Actual sampling time to reach the maximum observed plasma analyte concentration.
AUC_{24h}	Area under the plasma analyte concentration-time curve from time 0 to 24 hours postdose, calculated by linear-linear trapezoidal summation.
AUC_{last}	Area under the plasma analyte concentration vs time curve from time 0 to time of the last measurable (non-below quantification limit [BQL]) concentration calculated by linear-linear trapezoidal summation.
AUC_{∞}	Area under the analyte concentration vs. time curve from time 0 to infinite time, calculated as $AUC_{\text{last}} + C_{\text{last}}/\lambda_z$, where C_{last} is the last observed measurable (non-BQL) plasma analyte concentration; extrapolations of more than 20.00% of the total AUC are reported as approximations.
$t_{1/2}$	Apparent elimination half-life calculated as $0.693/\lambda_z$
λ_z	Apparent terminal elimination rate constant, estimated by linear regression using the terminal log-linear phase of the log transformed concentration-time curve.

8.5. Genetics and Pharmacogenomics

Participation in pharmacogenomic research is optional. A pharmacogenomic (DNA) blood sample will be collected, preferably at baseline, from participants who consent separately to this component of the study to allow for pharmacogenomic research, where local regulations permit.

Genetic (DNA) variation may be an important contributory factor to interindividual variability in drug response and associated clinical outcomes. Genetic and epigenetic factors may also serve as markers for disease susceptibility and prognosis and may identify population subgroups that respond differently to an intervention.

The optional pharmacogenomic samples may be analyzed for identification of genetic and epigenetic factors that may be associated with the disease and/or the response to JNJ-77242113. This research may consist of the analysis of one or more candidate genes, or the analysis of genetic and epigenetic markers throughout the genome, or analysis of the entire genome (as appropriate) in relation to the disease and the treatments. Whole blood samples of approximately 6 mL will be collected for the genetic and pharmacogenomics analyses.

These analyses will be performed at the sponsor's discretion and may be reported separately.

8.6. Biomarkers

Biomarker assessments will be used to define and identify PD markers of therapeutic response to better understand the mechanism of action of JNJ-77242113 in participants with psoriasis, and aid in evaluating the drug exposure clinical response relationship, and the pathophysiology of psoriasis. This will include evaluation of relevant disease and pathway engagement biomarkers in skin, serum, whole blood and PBMCs. These assessments could also help explain inter-individual variability including differences between responders and non-responders to support patient stratification. Biomarker samples may also be used to help address emerging issues and to enable the development of safer, more effective, and ultimately individualized therapies as well as development of tests/ assays related to JNJ-77242113 and psoriasis.

Biomarker samples will be collected per the Schedule of Activities (Section 1.3). Instructions for collection and shipment of samples will be outlined in the Laboratory and Biopsy reference manuals and will include the following assessments.

Stopping Analysis

Biomarker analyses are dependent upon the availability of appropriate biomarker assays and clinical response rates. Biomarker analysis may be deferred or not performed, if during or at the end of the study, it becomes clear that the analysis will not have sufficient scientific value for biomarker evaluation, or if there are not enough samples or responders to allow for adequate biomarker evaluation. In the event the study is terminated early or shows poor clinical efficacy, completion of biomarker assessments is based on justification and intended utility of the data.

8.6.1. Ex vivo whole blood cytokine release assay

An optional ex vivo whole blood IL-23 induced cytokine release assay will be used to measure systemic PD activity from inhibition of IL-23 induced signaling as it relates to exposure to confirm systemic IL-23 pathway engagement with JNJ-77242113 in participants with psoriasis.

8.6.2. Serum Psoriasis Pharmacodynamic Changes

Inflammatory mediators relevant to the pathophysiology of psoriasis including but not limited to IL-22, IL-17A, IL-17F and beta-defensin-2 will be evaluated to assess the impact of JNJ-77242113 on inflammatory proteins in the serum.

8.6.3. Skin Psoriasis-Associated Gene Expression Changes

Total RNA will be extracted from lesional and non-lesional skin biopsies to assess impact of JNJ-77242113 on psoriasis-associated gene signatures and individual genes to better define the therapeutic response. Non-invasive tape strip sampling will be performed as an additional approach to characterize JNJ-77242113 driven skin transcriptional changes in participants with psoriasis.

8.6.4. Flow cytometric analysis

Peripheral blood mononuclear cells isolated from whole blood will be used to determine the impact of JNJ-77242113 on psoriasis-relevant immune cell subset distribution changes in the periphery.

8.7. Immunogenicity Assessments

Antibodies to JNJ-77242113 will be evaluated in serum samples collected from all participants according to the SoA. Additionally, serum samples should also be collected at the final visit from participants who discontinued study intervention or were withdrawn from the study. These samples will be tested by the sponsor or sponsor's designee.

Serum samples will be screened for antibodies binding to JNJ-77242113 and the titer of confirmed positive samples will be reported. Other analyses may be performed to verify the stability of antibodies to JNJ-77242113 and/or further characterize the immunogenicity of JNJ-77242113.

Serum samples will be used to evaluate the immunogenicity of anti-JNJ-77242113 antibodies. Samples collected for immunogenicity analyses may additionally be used to evaluate safety or efficacy aspects that address concerns arising during or after the study period. Genetic analyses will not be performed on these serum samples. Participant confidentiality will be maintained.

Analytical Procedures

The detection and characterization of antibodies to JNJ-77242113 will be performed using a validated assay method by or under the supervision of the sponsor. All samples collected for detection of antibodies to JNJ-77242113 will also be evaluated for corresponding JNJ-77242113 plasma concentration to enable interpretation of the antibody data. Antibodies may be further characterized and/or evaluated for their ability to neutralize the activity of the study intervention(s). Samples may be stored up to 15 years (or according to local regulations) following

the last participant's last visit for the study at a facility selected by the sponsor to enable further analysis of immune responses to JNJ-77242113.

8.8. Medical Resource Utilization and Health Economics

Health Economics/Medical Resource Utilization and Health Economics parameters are not evaluated in this study.

9. STATISTICAL CONSIDERATIONS

Statistical analysis will be done by the sponsor or under the authority of the sponsor. A general description of the statistical methods to be used to analyze the efficacy and safety data is outlined below. Specific details will be provided in the Statistical Analysis Plan.

9.1. Statistical Hypotheses

The hypothesis of this study is that there is a dose response relationship for JNJ-77242113 in the proportion of participants achieving a PASI 75 response at Week 16.

9.2. Sample Size Determination

This study is designed to enroll approximately 240 participants, in order to provide sufficient data to have adequate power to detect a JNJ-77242113 dose-response signal for the proportion of participants achieving PASI 75 at Week 16 using the Multiple Comparison Procedures with modeling techniques (MCP-Mod) method.

The sample size of 240 participants was also chosen in order to have sufficient power to detect a difference between the JNJ-77242113 groups and the placebo group for the primary endpoint of the proportion of participants achieving PASI 75 at Week 16.

The assumptions for the sample size and power calculations specified below were mainly based on the clinical data from the guselkumab Phase 2 and Phase 3 clinical studies that evaluated the safety and efficacy of guselkumab in the treatment of adult participants with moderate-to-severe plaque psoriasis.

The null hypothesis of no dose-response relationship is to be tested at an overall Type 1 error rate of 0.05 (2-sided). Assuming a PASI 75 response rate of 6% and 70% in the placebo and JNJ-77242113 highest dose groups, respectively, a sample size of approximately 40 participants in the placebo group and each of the JNJ-77242113 treatment groups will provide an average power of at least 90% to detect a dose-response signal across different candidate dose-response models (to be detailed in the SAP).

Furthermore, assuming PASI 75 response rates at Week 16 are 5% to 10% for placebo, 30% to 80% for the JNJ-77242113 dose groups, respectively, with 40 participants in each of the treatment groups, approximately 240 participants are planned to be randomized in equal ratio to the placebo and each of JNJ-77242113 dose groups (n=40/arm), this study provides:

- At least 90% power to detect a 35% treatment difference between the JNJ-77242113 treatment groups (n=40) and the placebo group (n=40) in the proportion of participants who achieve a PASI 75 response at Week 16 at a significant level of 0.05 (2-sided) based on a 2-sample Z-test.

9.3. Populations for Analysis Sets

For purposes of analysis, the following populations are defined:

For the efficacy analyses in this study, the full analysis set (FAS) will be used according to the participants' assigned treatment to which they were randomized, regardless of the treatment they actually received. The FAS includes all randomized participants who receive at least 1 administration of study intervention. The FAS will be used for all primary and secondary efficacy analyses.

Safety analyses will include all randomized participants who received at least 1 administration of study intervention and participants will be analyzed based on the treatment they actually received, regardless of the treatment groups to which they were assigned. Pharmacokinetics analyses for JNJ-77242113 will include all randomized participants who receive at least 1 complete dose of JNJ-77242113 and have at least 1 valid blood sample drawn for PK analysis after their first dose of JNJ-77242113. Antibodies to JNJ-77242113 will be analyzed for all randomized participants who receive at least 1 dose of JNJ-77242113 and have at least 1 sample obtained after the first dose of JNJ-77242113 for the detection of antibodies to JNJ-77242113.

Population	Description
Enrolled	All participants who sign the ICF
Randomized	All participants who were randomized in the study
FAS	All randomized participants who take at least 1 dose of study intervention
Safety Analysis Set	All randomized participants who take at least 1 dose of study intervention.
PK Analysis Set	All randomized participants who received at least 1 complete dose of JNJ-77242113 and had at least 1 valid blood sample drawn for PK analysis after their first dose of JNJ-77242113
Immunogenicity Analysis Set	All randomized participants who received at least 1 dose of JNJ-77242113 and who had at least 1 sample obtained after the first dose of JNJ-77242113 for the detection of antibodies to JNJ-77242113

9.4. Statistical Analyses

9.4.1. Statistical Methods

Simple descriptive summary statistics, such as n, mean, standard deviation (SD), median, interquartile range, minimum, and maximum for continuous variables, and counts and percentages for discrete variables will be used to summarize most data.

To assess the primary objective of the dose response profile of JNJ-77242113 dose groups and facilitate the selection of JNJ-77242113 doses and dosing regimen for future studies, Multiple

Comparison Procedures with modeling (MCP-Mod) techniques will be used to analyze the primary endpoint, the proportion of participants achieving PASI 75 at Week 16.

In addition, for binary response efficacy endpoints, comparisons between each of the JNJ-77242113 groups versus placebo will be performed using a Cochran-Mantel-Haenszel (CMH) test stratified by the baseline weight (≤ 90 kg, > 90 kg). For continuous efficacy endpoints, treatment comparisons will be performed using a Mixed-Effect Model Repeated Measure (MMRM) model. The MMRM model will have treatment group, baseline weight (≤ 90 kg, > 90 kg), and baseline value for the corresponding efficacy endpoint as explanatory factors. The MMRM model will also include visit, treatment group by visit interaction, baseline weight (≤ 90 kg, > 90 kg) by visit interaction, and baseline value by visit interaction as additional explanatory factors. The Least Square mean (LSmean) estimates and their corresponding 95% confidence interval (CI) will be provided at each time point. In addition, the estimates of LSmean difference and 95% CIs between the JNJ-77242113 groups and placebo will be provided.

In general, all statistical testing will be performed at a significance level of 0.05 (2-sided) unless otherwise specified. Nominal p-values will be displayed for all treatment comparisons.

9.4.2. Efficacy Analyses

9.4.2.1. Primary Endpoint(s)

The primary efficacy endpoint is the proportion of participants achieving PASI 75 response at Week 16, defined as at least a 75% reduction from baseline in PASI total score.

9.4.2.1.1. Estimand

9.4.2.1.1.1. Primary Estimand

The primary estimand (ie, a precise definition of the primary targeted treatment effect) is defined by the following 5 attributes:

Study intervention:

- JNJ-77242113 25 mg QD, 50 mg QD, 25 mg BID, 100 mg QD, and 100 mg BID
- Placebo

Population: adult participants with moderate to severe plaque psoriasis

Variable/endpoint: Response binary variable, where a responder is defined as a participant achieving a PASI 75 response at Week 16 who does not have intercurrent events in categories 1-2 (defined below).

Intercurrent Events (ICEs) and their corresponding strategies

ICEs	Analysis Strategy for Addressing Intercurrent Events
1. Discontinuation of study intervention due to lack of efficacy or due to an AE of worsening of psoriasis	Composite Strategy: Participants with these intercurrent events are considered as PASI 75 non-responders after these events, and prior to Week 16. The occurrence of these intercurrent events is captured in the variable definition.

2. Initiation of a protocol-prohibited medication or therapy during the study that could improve psoriasis	
3. Discontinuation of study intervention for reasons other than ICE 1	Treatment Policy: observed data will be used regardless of whether or not this intercurrent event had occurred.

Note: For participants experiencing multiple ICEs, ICE 2 will override ICE 3.

Population level summary: Difference in the proportions of participants achieving a PASI 75 response at Week 16 between the JNJ-77242113 and placebo intervention groups.

Primary Endpoint Analysis

In the primary efficacy analysis, data from all randomized participants who received at least 1 administration of study intervention will be analyzed according to their assigned treatment group.

A unified strategy that combines MCP-Mod techniques, will be used to analyze the dose-response relationship for the JNJ-77242113 doses in PASI 75 at Week 16. This approach consists of 2 major steps. The first step consists of testing the dose-response signal via multiple contrast tests while controlling the overall Type 1 error. If a dose-response signal is detected, the second step is to select a model that best describes the observed data, which may be used to support dose selection in future studies. In addition, a simple semi-parametric Bayesian normal dynamic linear model (NDLM) will also be explored to complement the frequentist MCP-Mod analysis. The details of the dose-response analysis will be provided in the SAP.

The study will be considered positive if a dose-response signal for the primary endpoint is detected. In addition to the dose-response analysis, pairwise comparisons of the JNJ-77242113 groups versus the placebo group will be performed for PASI 75 at Week 16; these comparisons will not be adjusted for multiplicity. For these comparisons, a CMH stratified by baseline weight category ($\leq 90\text{kg}$, $>90\text{kg}$) will be used. The proportion difference between each JNJ-77242113 group and placebo group and its 2-sided 95% CI will be provided based on normal approximation with Mantel-Haenszel weights adjusting for baseline weight category.

To examine the robustness of the primary endpoint analysis, additional analyses will be conducted using different missing data approaches; these analyses will be described in the SAP. In addition, sensitivity analyses will be performed for the primary endpoint using the per-protocol population, which includes participants who are generally compliant with the protocol. To evaluate the consistency of the efficacy, subgroup analyses of the primary endpoint will be performed.

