3. SAMPLE SIZE DETERMINATION

3.1. 77242113PSO2001

This study is designed to enroll approximately 240 participants, in order to provide sufficient data to have adequate power to detect a JNJ-77242113 dose-response signal for the proportion of participants achieving PASI 75 at Week 16 using the Multiple Comparison Procedures with modeling techniques (MCP-Mod) method.

The sample size of 240 participants was also chosen in order to have sufficient power to detect a difference between the JNJ-77242113 groups and the placebo group for the primary endpoint of the proportion of participants achieving PASI 75 at Week 16.

The assumptions for the sample size and power calculations specified below were mainly based on the clinical data from the guselkumab Phase 2 and Phase 3 clinical studies that evaluated the safety and efficacy of guselkumab in the treatment of adult participants with moderate-to-severe plaque psoriasis.

The null hypothesis of no dose-response relationship is to be tested at an overall Type 1 error rate of 0.05 (2-sided). Assuming a PASI 75 response rate of 6% and 80% in the placebo and JNJ-77242113 highest dose groups, respectively, a sample size of approximately 40 participants in the placebo group and each of the JNJ-77242113 treatment groups will provide an average power of at least 95% to detect a dose-response signal across different candidate dose-response models. [Table 1](#) and [Table 2](#) below show the candidate dose response models and the power to detect a dose-response signal based on the primary endpoint of the proportion of participants achieving PASI 75 at Week 16 for various candidate models.

Table 1: Candidate Dose-response^a Models

Model Type	Model specification ^b
E _{max} 1	dose/(35+dose) (ED ₅₀ =35)
E _{max} 2	dose/(50+dose) (ED ₅₀ =50)
Logistic	1/{1+exp[(35-dose)/15]} (ED ₅₀ =35, δ=15)
SigEMax	Dose ³ /((35) ³ +dose ³) (ED ₅₀ =35, h=3)
Linear	dose
Quadratic	dose-0.002*(dose**2) (δ=-0.002)

^a Response is PASI 75 response at Week 16.
^b A standardized version of the dose response model

Table 2: Summary of powers for each candidate models

Sample size Per Group	Emax 1	Emax 2	Logistic	SigEMax	Linear	Quadratic	Mean Power
40	>95%	>95%	>95%	>95%	>95%	>95%	>95%

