Furthermore, assuming PASI 75 response rates at Week 16 are 5% to 10% for placebo, 30% to 80% for the JNJ-77242113 dose groups, respectively, with 40 participants in each of the treatment groups, approximately 240 participants are planned to be randomized in equal ratio to the placebo and each of JNJ-77242113 dose groups (n=40/arm), this study provides:

At least 90% power to detect a 35% treatment difference between the JNJ-77242113 treatment groups (n=40) and the placebo group (n=40) in the proportion of participants who achieve a PASI 75 response at Week 16 at a significant level of 0.05 (2-sided) based on a 2-sample Z-test.

3.2. 77242113PSO2002

Protocol 77242113PSO2002 is the LTE study of Protocol 77242113PSO2001, therefore there is no formal calculation of the sample size for study 77242113PSO2002. The sample size of this LTE study will be determined by the number of participants who enroll in study 77242113PSO2001 and are eligible to enter and choose to participate in this LTE study.

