The gMCP-Mod procedure extends the MCP-Mod methodology to non-continuous endpoints. This is accomplished by decoupling the dose-response model from the expected response through the use of an ANOVA style parameterization of the dose-response parameter. For the binary endpoint used in this study, a logistic regression of the event proportion at each dose level will be used. After this first step, the mean parameter estimates from the logistic model and the corresponding covariance matrix, both of which are on the logit scale, will then be used during the rest of the gMCP-Mod procedure. Point estimates from the selected models will be displayed on the proportion scale in all statistical outputs.

Candidate Models and Multiple Testing Procedure

There are six candidate models (Section 3.1) that will be considered for the primary analysis. These are 2 Emax models ($ED_{50} = 35$ mg and 50 mg respectively), logistic model ($ED_{50} = 35$ mg, $\delta=15$), SigEMax model ($ED_{50} = 35$ mg, $h=3$), linear model, and quadratic model ($\delta=-0.002$) where dose-response will be tested using dose levels of 0 (placebo), and JNJ-77242113 treatment groups⁴.

The gMCP-Mod procedure requires certain parameter estimates be pre-specified for the candidate models based on available information in order to derive optimum contrast coefficients for testing the null hypothesis: that a dose-response does not exist in any of the candidate models. It is through testing this hypothesis that the model which best describes the dose-response relationship will be identified. The parameters used to determine the contrast for testing will assume a placebo PASI 75 rate of 6% and maximum treatment effect be 74% (placebo-adjusted).

The gMCP-Mod procedure for non-continuous endpoints diverges from the original MCP-Mod procedure in the calculation of the optimum contrast coefficients. The gMCP-Mod methods that will be used to calculate the optimum contrast coefficients require the pre-specified model parameters from above along with the covariance matrix from the logistic regression in the first step. In practice, since the covariance matrix in the first step is based on actual data, the optimum contrast coefficients are recalculated when the actual data become available. The parameter estimates for the candidate models, however, will remain fixed.

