In addition to the dose-response analysis, pairwise comparisons of each JNJ-77242113 treatment group versus the placebo group will be performed for the primary endpoint of PASI 75 at Week 16. Pairwise comparisons will not be adjusted for multiplicity. The Cochran-Mantel-Haenszel chi-square statistic stratified by baseline weight category (≤ 90 kg, > 90 kg) at a 2-sided significance level of 0.05 will be used. Difference in response rates between each of the active groups and the placebo group adjusted for baseline weight category (≤ 90 kg, > 90 kg) using Mantel-Haenszel weight and the corresponding 95% CI will be presented.

In addition, the proportion of participants achieving a PASI75 response at Week 16 by investigator site will be summarized.

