6.2. Appendix 2 Changes to Protocol-Planned Analyses

N/A

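### The planned Mantel-Haenszel 95% CI for each PASI 75 difference covers about 93.6% on average, and at 70-80% active response its lower limit is too high about 5% of the time instead of 2.5%

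*Protocol*

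**What the plan says.** Protocol 9.4.2.1.1.1 (Primary Endpoint Analysis) pairs each active dose with placebo for PASI 75 at Week 16. It uses a CMH test stratified by baseline weight (90 kg or less, above 90 kg), without multiplicity adjustment. For the difference in proportions, a "2-sided 95% CI will be provided based on normal approximation with Mantel-Haenszel weights adjusting for baseline weight category".

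SAP 5.3.1.2.3.1 (Pairwise Comparisons) repeats the weighting: the difference is adjusted "using Mantel-Haenszel weight and the corresponding 95% CI will be presented". Neither document names the variance estimator.

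The planning rates are in SAP 3.1: "assuming PASI 75 response rates at Week 16 are 5% to 10% for placebo", and 30% to 80% for the active groups, "with 40 participants in each of the treatment groups" (also Protocol 9.2). For the dose-response calculation SAP 3.1 goes further: "Assuming a PASI 75 response rate of 6% and 80% in the placebo and JNJ-77242113 highest dose groups". SAP 5.3.1.2.3 builds the contrasts on the same values, 6% plus 74 points. Protocol 9.2 has 70% at the highest dose.

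The SAP provides exact intervals in two other places: for rare events among the secondary binary endpoints (5.4.1.3.1) and for subgroups (5.7.5). Neither applies to the primary pairwise comparisons.

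**The concern.** With 40 per arm, a placebo rate near zero and an active rate of 70-80%, a symmetric normal-approximation interval for a difference in proportions sits badly. The estimate and its standard error are correlated, and the sampling distribution of a large difference is skewed. The interval is then placed too far from zero, so the errors collect at the lower limit.

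The primary estimand is summarised as a difference in proportions, and this interval is its reported uncertainty at each dose. Readers take the lower limit as the smallest credible benefit. If it is too high twice as often as stated, the benefit is overstated at the most effective doses, which are the likeliest to go forward.

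**Working it through.** **Inputs.** 40 per arm; placebo 5-10%, active 30-80% (SAP 3.1, Protocol 9.2). Two weight strata (Protocol 9.4.2.1.1.1). Missing Week 16 data count as non-response (SAP 5.3.1.2.3), so the analysed number stays near 40 per arm. Stratum sizes are not given; the main calculation assumes 20/20 in each arm with a common rate in both strata.

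**The plan's own figure.** The documents state no coverage. The nearest figure is at least 90% power for a 35-point difference by a two-sample Z-test. Power = Φ{[d − 1.96√(2p̄(1−p̄)/n)] / √(p1(1−p1)/n + p0(1−p0)/n)}. At placebo 5% and active 40%, p̄ = 0.225, and (0.35 − 1.96 × 0.0934)/0.0848 = 1.97, giving 97.6%. At placebo 6% and 10% it is 97.1% and 95.4%. The stated power holds.

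**The planned interval.** Estimate = Σw(p1 − p0)/Σw over strata, with w = n1n0/(n1 + n0). Unpooled variance = Σw²[p1(1−p1)/n1 + p0(1−p0)/n0]/(Σw)². Limits = estimate ± 1.96 SE.

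**Coverage.** All outcomes were enumerated exactly at 121 rate pairs: placebo 5-10% in steps of 0.5 points, active 30-80% in steps of 5 points. A lower miss means the lower limit exceeds the true difference; an upper miss means the upper limit falls below it.

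| | Planned, unpooled | Stratified Miettinen-Nurminen |
|---|---|---|
| Coverage range | 90.8-94.2% | 94.3-96.0% |
| Mean coverage | 93.6% | 95.0% |
| Pairs under 95% | 121 of 121 | 60 of 121 |
| Pairs under 93% | 15 | 0 |
| Pairs under 92% | 4 | 0 |
| Lower/upper misses, 30-45% active | 3.0/3.1% | 2.6/2.4% |
| Lower/upper misses, 50-65% active | 4.0/2.4% | 2.3/2.6% |
| Lower/upper misses, 70-80% active | 5.2/1.7% | 2.1/2.9% |
| Mean gap between lower and upper misses | 1.69 points | 0.45 points |

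The Miettinen-Nurminen column uses the constrained maximum-likelihood variance per stratum, the factor N/(N−1), and Mantel-Haenszel weights.

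**Sensitivity to the variance estimator.** Mean coverage is 94.2% with n−1 variance and 93.9% with Sato. Lower misses at 70-80% active stay at 4.7-4.8% and 4.9-5.1%.

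**Sensitivity to the strata.** With splits of 24/16 and 28/12, mean unpooled coverage is again 93.6% and the lower miss at 70-80% active 5.2-5.3%. With strata of 26/14 or 30/10, unequal arm splits (23/17 against 19/21) and a weight odds ratio of 0.5 or 0.35, the planned interval covers 91.5-94.3% and Miettinen-Nurminen 94.6-96.4%.

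**How often the affected range arises.** Under the SAP's six candidate curves (6% placebo, 80% maximum, Table 5 doses), 10 of the 30 dose-by-curve rates are 70% or more, whether the curve is placed on the logit or the proportion scale. Lower misses there average 5.0% (4.2-6.8%).

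**Two data examples.**
- 32/40 against 2/40: difference 75.0 points. SE = √(0.80 × 0.20/40 + 0.05 × 0.95/40) = 0.0720, so the planned CI is 60.9 to 89.1. Miettinen-Nurminen gives 57.5 to 86.1.
- 12/40 against 2/40: difference 25.0 points. SE = √(0.30 × 0.70/40 + 0.05 × 0.95/40) = 0.0802, so the planned CI is 9.3 to 40.7. Miettinen-Nurminen gives 9.0 to 41.5.

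**The case against.** The strongest case on the other side is that this is small and nothing turns on it. "The study will be considered positive if a dose-response signal for the primary endpoint is detected" (Protocol 9.4.2.1.1.1), and the pairwise comparisons are unadjusted and judged by CMH p-values. No threshold in the documents lies near 60.9 or 57.5 points. That stands, and it is why the point is rated low.

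The unpooled variance is also the least favourable of three that the text allows. At exactly 6% against 80%, coverage is 93.8% unpooled, 94.6% with n−1 and 94.8% with Sato, with lower misses of 4.8%, 4.2% and 3.9%. At that point the excess is nearer 1.6-1.7 times nominal under the two milder estimators. But 6% against 70% and 75% are worse, with lower misses of 4.1-5.6%, and the average over the 70-80% range stays close to 5% under every estimator.

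The lowest coverages are partly effects of discreteness: 93.8% at 6/80% falls to 90.8% at 6.5/80%. The minimum and the count under 92% should carry little weight; the averages are stable across strata.

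Twenty of the 30 dose-by-curve rates are below 70%, and at 30-45% active the misses are balanced. Both are true, and the one-sidedness is claimed only for high active rates.

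Finally, the change touches linked analyses. The imputation-based supplementary analyses (SAP 5.3.1.2.5) pool Mantel-Haenszel differences over 500 datasets, and a score interval supplies no standard error for the usual pooling. Those intervals are specified separately and can stay as written. The per-protocol analysis (SAP 5.3.1.2.6) takes its method from 5.3.1.2.3 and would follow the change.

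**Conclusion.** The concern holds, at low severity. At the plan's own rates and sample size, the nominal 95% interval covers about 93.6% on average with unpooled variance (93.9-94.2% with the alternatives). At 70-80% active response its lower limit is too high about 5% of the time, twice the nominal rate. The fault is mainly the interval's position rather than its width: the mean width of the Miettinen-Nurminen interval is only 0.1-4.1% larger.

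The result assumes about 40 analysed per arm and the planned rates. The stratum split is an assumption, but varying it hardly moves the averages. Secondary endpoints were not computed. The dose-response test, the CMH p-values and any superiority conclusion are unaffected.

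**What to change.** In SAP 5.3.1.2.3.1, keep the Mantel-Haenszel point estimate and the CMH test. Name the stratified Miettinen-Nurminen score interval with Mantel-Haenszel weights for all five pairwise PASI 75 differences, whatever rates are observed, and leave no choice of method open. State that the imputation-based intervals of SAP 5.3.1.2.5 remain as written and that the per-protocol analysis follows the new method. If the interval is extended to any secondary endpoint, list it by name before unblinding.

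Adding 0.5 per cell is not proposed. It restores total coverage (94.4-95.8%) but unbalances the misses at 30-45% active (1.5/3.5%), and its mean gap between lower and upper misses is 2.01 points.

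The cost is one SAP sentence plus the clarification above, an iterative calculation, and an entry under "Changes to Protocol-Planned Analyses" (SAP Appendix 2, now marked not applicable). There are three downsides:
- The interval is not centred on the estimate.
- On average the lower limit moves by −0.1 point at 5/30%, −2.3 at 6/70% and −3.2 at 6/80%; the upper limit moves by +1.0, −2.2 and −2.8.
- Coverage remains slightly under 95% at 60 of 121 pairs (minimum 94.3%), and upper-limit misses reach 3.45% at worst.
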